**Table 1. SPIRIT Depiction of Timing and Measures Collected for Implementation Phase**

[figure not shown]
	Screening	Post-Training	Pre-Treatment	Mid-Treatment	Post-Treatment	6-Months Post-Treatment
Patient						
Sociodemographics			X		X	X
Eligibility Items	X					
PROMIS-SD P	X		X	X	X	X
PROMIS-SRI			X	X	X	X
DSM-5 Cross-Cutting			X		X	X
SDS			X		X	X
Sleep Health Composite			X	X	X	X
PHENX Toolkit			X		X	X
CEQ					X	
Provider						
Sociodemographics		X				
Occupation		X				
Acceptability P		X		X	X	
Appropriateness		X		X	X	
Feasibility		X		X	X	
Number of Sessions					X	

*Note.* Allocation to Adapted or Standard TranS-C occurs at the county level and prior to enrollment of any participants in that county (i.e., patients or providers). Enrollment of patients and allocation to immediate TranS-C or delayed TranS-C (UC-DT) occur after the screening and before the pre-treatment assessment. Enrollment of providers after the training. P = Primary Outcome. PROMIS-SD = PROMIS-Sleep Disturbance; note: PROMIS-SD is only assessed during the pre-treatment assessment if done more than one month after the screening to minimize burden for patients. PROMIS-SRI = PROMIS-Sleep Related Impairment. SDS = Sheehan Disability Scale. CEQ = Credibility/Expectancy Questionnaire

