## 2 AIMS

Together, the goal of the present hybrid type 2 effectiveness-implementation study [48, 49] is to evaluate the implementation and effectiveness outcomes of TranS-C in CMHCs of counties across California in the United States. The study will be conducted in three phases. This protocol will focus on Phase 1, the Implementation Phase, during which TranS-C is implemented in CMHCs via facilitation (see Method). Phase 2 is the Train-the-Trainer Phase, during which CMHC providers learn to train and supervise their peers in the delivery of TranS-C. Phase 3 is the Sustainment Phase, during which we will assess the extent to which TranS-C activities are sustained after facilitation has ceased.

During the Implementation Phase, sites are cluster-randomized by county to Adapted TranS-C or Standard TranS-C with 1:1 allocation. Then, within each county, patients are randomized to immediate TranS-C or UC-DT. The first aim is to assess the effectiveness of TranS-C, compared to UC-DT. We hypothesize that, compared to UC-DT, TranS-C (combined Adapted and Standard) will be associated with larger reductions in the primary patient outcome of sleep disturbance and the secondary patient outcomes of sleep-related impairment, functional impairment, and psychiatric symptoms. We also hypothesize that TranS-C's benefits for functional impairment and psychiatric symptoms will be mediated by improvements in sleep and circadian problems. The second aim is to evaluate whether TranS-C treatment condition (Adapted versus Standard TranS-C) is associated with fit to the CMHC context, operationalized as provider ratings of acceptability, appropriateness, and feasibility. We hypothesize that

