### 3.8 Sample Size

Sample size was determined via power analyses with Optimal Design [85, 86] and Stata 15 [87] and a two-sided alpha of 0.05. We used the original  $N = 8$  counties that agreed to participate, though as noted above, new counties have since been recruited to meet sample size goals determined by the following calculations. For Aims 1 and 3, 60 patients from eight randomized clusters/CMHCs was found to provide over 90% power to detect large effects (average  $d=0.89$  from [35]) between TranS-C and UC-DT, and over 80% power to detect a medium effect ( $d=0.50$ ) between Standard and Adapted TranS-C. For Aim 2, based on a prior study with a similar aim/measure [88], we expected a large effect size ( $d=0.80$ ) between Standard and Adapted TranS-C on the primary outcome of acceptability. Prior studies have reported high correlation coefficients between acceptability, feasibility, and appropriateness ( $rs=.67-.90$ ) [75, 89], thus the analysis for acceptability was expected to sufficiently power the other outcomes. Based on the site intra-class correlation (ICC) estimated from similar prior studies [90, 91], we assumed the ICC to be 0.01 and the inflation factor was calculated as  $1+(n-1)\times ICC$ . Eight clusters with an average cluster size of 10 was found to be needed to achieve over 80% power to detect a large effect for the outcome (acceptability) at the provider level. Thus, to test this aim, we would need at least 80 CMHC providers: 10 providers from 8 CMHCs (at least 4 CMHCs per randomized arm).

In sum, we aimed to randomize at least eight CMHC clinics to either Standard or Adapted TranS-C, with at least 80 providers (10 per CMHC). The goal for patients is 240 patients (30 per CMHC) randomized to immediate Standard or Adapted TranS-C and 240 randomized to UC-DT (30 per CMHC). Adding 20% to account for attrition, the total target sample size for providers is 96 and for patients is 576.

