## 4 PLANNED ANALYSES

### 4.1 Preliminary Analyses and Missing Data

Analyses will use all available data (intent-to-treat) [93]. If dropout is related to other variables, they will be included as predictors. Baseline between-group differences on demographic variables will be examined. These tests will not be used to select covariates in the primary intention-to-treat analysis [94-97]. Instead, covariates will be carefully selected at the conclusion of the trial—given the variations due to COVID-19 and the CMHC context (see Discussion)—and the potential influences of baseline differences will be evaluated as moderators (approach to moderation described below). Analyses comparing TranS-C to UC-DT will evaluate change in outcomes from pre-treatment to post-treatment. Analyses comparing Adapted to Standard TranS-C will evaluate change in outcomes from pre-treatment to post-treatment and pre-treatment to 6FU (see Method and Discussion for more details).

Distributions will be evaluated to detect outliers, and we will ensure that assumptions of planned analyses are met. Covariates will include the patient variables for which we stratified (i.e., age and presence of psychosis or substance use). For all statistical models, counties will be entered as dummy variables rather than a level of analysis due to the relatively small number of clusters. The average intraclass correlation on provider and patient level outcomes will be reported. The Benjamini–Hochberg procedure [98] will be used to correct for multiple testing for confirmatory analyses on the primary outcomes (i.e., sleep disturbance and acceptability) [99].

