#### **4.4 Aim 2: Adapted TranS-C versus Standard TranS-C on Fit to CMHC Context**

MLM will be used to account for multiple observations nested within providers. TranS-C treatment condition (Adapted versus Standard TranS-C) will be evaluated as a predictor of fit, operationalized as provider ratings of acceptability, feasibility, and appropriateness. The level 1 equation will include dummy-coded time indicators as the predictor (0 = pre-treatment, 1 = post-treatment). The level 2 equation will include dummy-coded treatment condition (0 = Standard TranS-C, 1 = Adapted TranS-C), treatment by time interaction terms, and dummy-coded counties (0 = Alameda, 1 = Contra Costa, 2 = Kings, 3 = Monterey, 4 = Placer, 5 = Santa Cruz, 6 = Solano, 7 = Santa Clara, 8 = Santa Barbara, and 9 = Lake) as predictors. The treatment effects of interest will be significant treatment by time interactions at the 5% level on the primary outcome of acceptability and the secondary outcomes of feasibility and appropriateness, all modeled as continuous variables. Significant treatment by time interactions indicate that change in perceptions of fit is significantly different comparing Adapted to Standard TranS-C. Significant interactions will be interpreted using planned contrasts (i.e., treatment effects on change from pre-treatment to post-treatment) and graphs.

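### The primary Aim 2 test of Adapted against Standard TranS-C has no county-level error term, although county is the unit randomized.

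*Combined protocol and SAP*

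**What the plan says.** Randomization of the two TranS-C versions is by county. Section 2 states that "sites are cluster-randomized by county to Adapted TranS-C or Standard TranS-C with 1:1 allocation", and the note to Table 1 adds that "Allocation to Adapted or Standard TranS-C occurs at the county level and prior to enrollment of any participants in that county". Section 3.7 says this randomization is unstratified.

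Section 4.1 sets the rule for the analysis: "For all statistical models, counties will be entered as dummy variables rather than a level of analysis". The reason given is the small number of clusters. The ICC is to be reported, but nothing feeds it into a test.

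Section 4.4 gives the Aim 2 model. On nesting: "MLM will be used to account for multiple observations nested within providers". The level 2 terms include condition coded "0 = Standard TranS-C, 1 = Adapted TranS-C), treatment by time interaction terms, and dummy-coded counties". On the test: "The treatment effects of interest will be significant treatment by time interactions at the 5% level on the primary outcome of acceptability". Acceptability is one of the two primary outcomes entering the Benjamini-Hochberg correction.

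Section 3.8 takes clustering into account when sizing Aim 2. "Based on the site intra-class correlation (ICC) estimated from similar prior studies", the text continues, "we assumed the ICC to be 0.01 and the inflation factor was calculated as" 1 + (n − 1) × ICC.

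None of the three sets of sensitivity analyses in section 4.6 concerns clustering.

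**The concern.** Providers in one county share a treatment version, local leadership and a way of being recruited (section 3.3.2: training is compulsory at some centers and voluntary at others). If mean change in acceptability varies between counties for such reasons, that variation is part of the error of the Adapted versus Standard contrast. A model with error only at provider and rating level treats roughly 80 to 100 providers as independently randomized when about ten counties were. The standard error is then too small and the p-value passed to the Benjamini-Hochberg step is too low.

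The dummies look like a remedy but are not one for this contrast. They suit Aim 1, where patients are randomized within county, and Aim 1 is not affected.

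**Working it through.** **Inputs from the documents.** Two-sided alpha 0.05, d = 0.80, ICC 0.01, 8 clusters of 10 providers, 80 providers needed and 96 targeted (3.8); 10 counties now taking part, most with three to 10 sites (3.3.1). **Assumed:** county ICC of change 0.05 and 0.10, county sizes, arm splits, a within-provider correlation of 0.5, 20% missing post ratings, and d read in SD units of change.

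**1. The plan's own power figure.** Design effect = 1 + 9 × 0.01 = 1.09. Noncentrality = 0.80 / √(4 × 1.09 / 80) = 3.43. With 8 − 2 = 6 df (critical value 2.447), power is 81.3%. With 9 per cluster it is 77.6%, so 10 is the smallest size above 80%, as section 3.8 says. A normal approximation on the effective sample size gives 92.9% and already passes 80% at 7 per cluster. The stated requirement is therefore best explained by cluster-level degrees of freedom.

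**2. What the dummies can do (10 counties).**

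| Design | Columns | Rank | Consequence |
|---|---|---|---|
| Aim 2: intercept, time, condition, condition × time, 9 county dummies | 13 | 12 | Condition main effect aliased; interaction estimable |
| The same plus 9 county × time dummies | 22 | 20 | Interaction aliased as well |
| Credibility regression (4.7) with county dummies | 11 | 10 | Condition not estimable |

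With complete pre and post ratings, the planned interaction test equals a two-sample t-test on provider change, and the dummies cancel exactly. With 20% of post ratings missing, they moved the interaction by 0.01 SD of change on average and its standard error by 0.2%. Extending the dummies to change would remove the contrast itself.

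**3. Type I error of the planned test.** Approximation: 2 × [1 − Φ(1.96 / √DE)], DE = 1 + (n − 1) × ICC. For 8 per county:

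- ICC 0.01: DE 1.07, 1.96 / 1.034 = 1.895, 5.8%
- ICC 0.05: DE 1.35, 1.96 / 1.162 = 1.687, 9.2%
- ICC 0.10: DE 1.70, 1.96 / 1.304 = 1.503, 13.3%

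Simulation (40,000 replicates per cell; last row 2,000 to 6,000):

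| Design | ICC 0.01 | 0.05 | 0.10 |
|---|---|---|---|
| 10 counties × 8 | 5.8% | 9.3% | 13.4% |
| 10 counties × 10 | 6.2% | 10.5% | 15.7% |
| 3, 4, 6, 9, 18 per arm | 6.4% | 11.5% | 17.3% |
| County dummies, 20% missing | 6% | 9% | 12–14% |

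**4. Tests with county-level error.** The t-test on county-mean change had a type I error of 4.6–5.1% with complete data. The mixed model with t on (counties − 2) df had 2.1–4.6% across the 10-county designs. With 8 × 10 at ICC 0.01 it is more conservative, at about 1.5%. Kenward-Roger df gave 0.3–4.2%.

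**5. Power for d = 0.80, 80 providers, 10 counties.**

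| Test and design | ICC 0.01 | 0.05 | 0.10 |
|---|---|---|---|
| Mixed model, equal 5:5 | 83% | 75% | 67% |
| Mixed model, 4, 6, 8, 10, 12 per arm | 82% | 74% | 65% |
| Mixed model, 3, 4, 6, 9, 18 per arm | 80% | 72% | 63% |
| Mixed model, 3:7 split | 76% | 68% | 59% |
| County means, equal 5:5 | 86% | 77% | 67% |
| County means, 4, 6, 8, 10, 12 per arm | 81% | 73% | 64% |
| County means, 3, 4, 6, 9, 18 per arm | 73% | 66% | 59% |
| County means, 3:7 split | 79% | 70% | 60% |

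The planned test has about 93% power at ICC 0.01, but at an inflated type I error. If each county were assigned by an independent 1:1 draw (assumed), a 3:7 or more uneven split would occur with probability 2 × (1 + 10 + 45 + 120) / 1024 = 34%.

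**The case against.** The strongest reply concerns size. The only ICC in the documents is 0.01, and there the excess is about one percentage point. Every larger figure needs an assumed ICC. Correcting that one point costs about 10 points of power with 10 × 8 (93% to 83%) and about 15 with 8 × 10 (93% to 78% for the mixed model). The choice of dummies was deliberate, because variance components are poorly estimated from few clusters. The county-mean t-test also holds its level more closely than the mixed model and has more power when counties are equal in size.

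Much of this stands as description. At ICC 0.01 the harm is small, and the power comparison should be visible to the sponsor. It does not rescue the test. The 0.01 is a site ICC for the outcome; the test depends on a county ICC of change, which the documents neither give nor bound. Section 3.8 reproduces only with cluster-level degrees of freedom, so the power cost was already accepted at the design stage. Few clusters are a reason to use a small-sample cluster method, not to leave the randomized unit out of the error. Either county-level test would be valid. The mixed model is preferred because it uses all available ratings, as section 4.1 requires, and keeps power better when counties are unequal.

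Section 3.8 calls its clusters CMHCs while allocation is by county, so the mismatch between sizing and analysis also involves different units.

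**Conclusion.** The concern holds: the confirmatory Aim 2 test omits the error of the randomized unit, and nothing else in the plan restores it. This should be fixed before analysis. The omission is certain; its effect depends on an unknown ICC. Type I error is about 6% at the documented ICC of 0.01. It reaches about 9–12% at 0.05 and 12–17% at 0.10, both assumed values, depending on county sizes and missing ratings.

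Two secondary points need clarifying. Read literally, the rule for all models in section 4.1 would make condition non-estimable in the exploratory credibility regression of section 4.7, although that section does not itself list the dummies. Section 4.5 gives no equations for Aim 3; a path on change scores or a single time point cannot contain both condition and fixed county dummies.

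**What to change.** - **4.1:** limit county dummies to Aim 1 and its moderator analyses (Exploratory Aim 2).
- **4.4:** drop the dummies and name one primary test: a mixed model with random provider, county and county-by-time effects, with condition by time tested by t on (counties − 2) df. Only this p-value for acceptability enters the Benjamini-Hochberg step. As sensitivity analysis, use a t-test of county-mean change on the same df.
- **4.7:** use county as the error unit for the Adapted versus Standard models.
- **4.5:** write out the Aim 3 equations and use a county-level interval with a small-sample correction. An uncorrected cluster-robust z-test would not do: for a simple contrast with 10 equal counties split 5:5, its type I error is P(|t on 8 df| > 1.96 × √0.8) = 11.8%, and it is 15–17% with strongly unequal counties or a 3:7 split.

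The cost is SAP wording and code, with no new data. Intervals become wider, on about 8 df, and power falls to the values tabulated above. With 100 providers and 20% of post ratings missing, the mixed model gives 85%, 80% and 68% at ICC 0.01, 0.05 and 0.10 with equal counties, and 85%, 76% and 67% with 5 to 15 providers per county.

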### 4.2 Dropout

The N by stage of dropout will be reported for the following: dropout after randomization but before the first treatment session, dropout after treatment has begun but attended half or fewer of the intended number of sessions (i.e.,  $\leq 2$  in Adapted,  $\leq 4$  in Standard), dropout after attended more than half the intended number of sessions (i.e.,  $> 2$  in Adapted,  $> 4$  in Standard) but before treatment has been completed, and dropout after treatment has been completed but prior to post-treatment or 6FU assessments. The number of patients who completed a post-treatment assessment but were lost to 6FU will also be reported. When available, the reasons for dropout and improvement among patients who drop out will be reported.

### 4.3 Aim 1: Effectiveness Outcomes of Standard or Adapted TranS-C versus UC-DT

Multilevel modeling (MLM) [100-102] will be used to account for multiple observations nested within

patient. The level 1 equation will include dummy-coded time indicators as the predictor (0 = pretreatment, 1 = post-treatment). The level 2 equation will include dummy-coded treatment condition (0 = UC-DT, 1 = Adapted or Standard TranS-C), treatment by time interaction terms, and dummy-coded counties (0 = Alameda, 1 = Contra Costa, 2 = Kings, 3 = Monterey, 4 = Placer, 5 = Santa Cruz, 6 = Solano, 7 = Santa Clara, 8 = Santa Barbara, and 9 = Lake) as predictors. The treatment effects of interest will be significant treatment by time interactions at the 5% level on the primary outcome of sleep disturbance and the secondary outcomes of sleep-related impairment, functional impairment, and psychiatric symptoms, all modeled as continuous variables. Significant treatment by time interactions indicate that change in patient outcomes is significantly different comparing Adapted or Standard TranS-C to UC-DT. Significant interactions will be interpreted using planned contrasts (i.e., treatment effects on change from pre-treatment to post-treatment) and graphs. Additionally, the indirect effects of TranS-C relative to UC-DT on functional impairment and psychiatric symptoms through improvements in sleep disturbance and sleep-related impairment will be tested using multilevel structural equation modeling [103].

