### 3.4 Interventions

Two variations of TranS-C are tested in the present research: Standard TranS-C and Adapted TranS-C. Both are delivered alongside the usual care offered by each CMHC. The control condition is usual care followed by delayed treatment with Adapted or Standard TranS-C (UC-DT). In the CMHCs, usual care consists of working with a service provider (e.g., psychologist, case manager, occupational therapist, psychiatrist, nurse practitioner) who provides direct mental health support from within their scope of practice. The patient might also be referred by that provider for other services as needed (e.g., healthcare, housing support, nutrition, vocational specialists, or peer advocacy). Occasionally patients receive treatment from interdisciplinary or residential teams, meaning their services are coordinated across multiple service providers. Although most providers delivered TranS-C via individual sessions, some chose to deliver it in a group setting. Note that TranS-C was originally developed in English, then translated into Spanish about four months into data collection to expand access and subsequently offered by Spanish-speaking providers. The treatment conditions, along with the adaptation process for Adapted TranS-C, are described below.

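### The Aim 1 model leaves out clustering of patients' change by TranS-C provider and delivery group, so its standard errors may be wrong, most likely too small.

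*Combined protocol and SAP*

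**What the plan says.** All references are to the combined protocol and SAP.

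- **Model.** In section 4.3, multilevel modelling "will be used to account for multiple observations nested within" patient. Time is at level 1; treatment, treatment by time and county dummies are at level 2. The effect of interest is the treatment-by-time interaction.
- **County.** Section 4.1 says "counties will be entered as dummy variables rather than a level of analysis", because there are few clusters. It adds the stratification covariates and says that the average ICC will be reported. It does not say that the ICC enters any model.
- **Shared providers.** Section 3.3.3 matches each patient to a TranS-C provider, ideally the patient's own. Section 3.8 targets 96 providers and 576 patients.
- **Groups.** Section 3.4 says that most providers delivered TranS-C individually but "some chose to deliver it in a group setting". The Discussion (section 5) lists this as a source of variance and leaves open whether such sources become covariates.
- **Delayed arm.** Under section 3.7, the provider of a delayed patient is asked to wait until the post-delay assessment is done. The same provider can therefore have patients in both arms.
- **ICC.** In section 3.8, "we assumed the ICC to be 0.01 and the inflation factor was calculated as" one plus cluster size minus one, times the ICC. This is a site ICC, used for the provider-level calculation for Aim 2.

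**The concern.** Patients treated by the same provider, or in the same group, may change by similar amounts. The eligible professions are mixed (section 3.2 names case managers, nurses and psychiatrists), so differences between providers in the change they produce are plausible. A model that treats patients as independent then misstates the variance of the treatment-by-time effect.

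Nothing else in the plan deals with this:

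- County dummies enter as main effects, so they shift levels and leave provider or group differences in change untouched.
- A covariate for delivery format would shift a mean without modelling correlation within a group.
- Reporting an ICC does not put it into the standard error.

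At stake are the interval and p-value for sleep disturbance, the primary patient outcome, whose p-value also enters the Benjamini–Hochberg correction. The secondary outcomes in 4.3 use the same model.

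**Working it through.** **Inputs from section 3.8.** The plan uses "a two-sided alpha of 0.05", with 240 immediate and 240 UC-DT patients before attrition and 80 providers. That is 240/80 = 3 treated patients per provider. After the attrition allowance it is 288/96 = 3 again.

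**Assumptions, not in the documents.** The provider or group ICC for change is taken as 0.01 to 0.15. The coefficient of variation (CV) of caseload is 0 or 1. Group size is 6.

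**The plan's own figure.** Section 3.8 says that "60 patients from eight randomized clusters/CMHCs was found to provide over 90% power to detect large effects", with d = 0.89. For n per arm, power = Φ(d/√(2/n) − 1.96).
- 240 per arm: above 0.999.
- 60 patients in total (30 per arm): 0.931.

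The claim reproduces on either reading.

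**Clustering in the treated arm only.** With two time points and complete data, the treatment-by-time effect is a comparison of mean change. The ICC here is therefore the share of variance in change that lies between providers or groups.

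- Treated-arm design effect: DE = 1 + ((1 + CV²)m − 1) × ICC, with m the mean cluster size.
- True SE / planned SE = √((1 + DE)/2).
- Type I error = 2 × (1 − Φ(1.96 / SE ratio)).

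With m = 3 and CV 0, DE = 1 + 2 × ICC. With m = 3 and CV 1, DE = 1 + 5 × ICC. If every treated patient were in an equal group of 6, DE is also 1 + 5 × ICC.

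| ICC | SE ratio, m = 3, equal | Type I error | SE ratio, CV 1 or groups of 6 | Type I error |
|---|---|---|---|---|
| 0.01 | 1.005 | 5.1% | 1.012 | 5.3% |
| 0.05 | 1.025 | 5.6% | 1.061 | 6.5% |
| 0.10 | 1.049 | 6.2% | 1.118 | 8.0% |
| 0.15 | 1.072 | 6.8% | 1.173 | 9.5% |

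Simulation agrees at ICC 0.05, 0.10 and 0.15: 5.5%, 6.1% and 7.0% for clusters of 3, and 6.6%, 7.8% and 9.3% for clusters of 6. In the last row the true SE is 17% larger than planned; put the other way, the planned SE is 1 − 1/1.173 = 15% too small.

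If only a quarter of treated patients were in groups of 6 and the rest were 3 to a provider, DE = 1 + (0.75 × 2 + 0.25 × 5) × ICC. The SE ratio is then 1.034 at ICC 0.05 and 1.067 at 0.10.

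**Providers working in both arms.** Let each provider have m patients per arm, with effects on change in both arms correlated r.
- True variance of a provider's between-arm difference: 2 × ICC × (1 − r) + 2 × (1 − ICC)/m.
- Planned variance: 2/m.
- With m = 3 and ICC 0.10, the SE ratio is 1.095 at r = 0, 1.025 at r = 0.5 and 0.949 at r = 1.
- Setting the two variances equal gives r = 1 − 1/m = 2/3.

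**Power after allowing for clustering.** In the last row of the table DE = 1.75, so SE = √((1 + 1.75)/240) = 0.107. Power is above 0.999 at d = 0.89, and Φ(0.50/0.107 − 1.96) = 0.997 at d = 0.50.

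**The case against.** The strongest objection concerns direction. A reader might infer that the planned standard errors are certainly too small. The documents do not support that. The TranS-C provider is ideally the patient's own provider (3.3.3), usual care consists of working with such a provider (3.4), delayed patients have a provider too (3.7), and patients are randomized within county rather than by provider. Effects shared across arms partly cancel, and above r = 2/3 the planned standard error is too large. This stands for provider effects. It does not reach delivery-group effects: delayed patients have not started TranS-C at the pre-to-post comparison, so those effects exist only in the treated arm. The same holds for differences in skill at delivering TranS-C.

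The second objection is size. No provider ICC for patient change is given. At the planned 3 patients per provider with equal caseloads the error is small, and most providers used individual sessions. This stands too. The upper figures need very uneven caseloads or widespread group delivery, and neither is documented. The plan does give reasons to expect uneven caseloads: training was compulsory at some sites and voluntary at others (3.3.2), and provider turnover was substantial (section 5). Larger figures, such as those from supposing that only half the providers treat patients, have no basis in the documents.

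A reader might also infer that the moderator tests in 4.8 carry the same error. For patient-level moderators such as age and sex this does not follow. A shared provider effect inflates the interaction's variance only as far as the moderator itself clusters by provider. In simulations with an unclustered moderator (240 per arm; clusters of 3 and 6; ICC 0.05 to 0.15), type I error for the moderator interaction stayed close to 5%.

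**Conclusion.** The omission is real: Aim 1 has no provider or delivery-group term and no cluster-robust variance, although shared providers and group delivery are both documented. The standard error of the primary patient comparison may therefore be wrong. It is too small for any positive delivery-group ICC, or where provider effects are specific to the treated arm. Otherwise the direction depends on how strongly provider effects are shared between arms.

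Under treated-arm clustering the effect runs from negligible (5.1%) to material (9.5%), and where the trial falls in that range cannot be told from the plan. Every ICC, caseload CV and group size used here is assumed. The planned effect of d = 0.89 would survive any of these corrections. The exposure is in results near p = 0.05, including secondary outcomes. The change should be made because it is cheap and gives more trustworthy intervals on a primary outcome, not because the main conclusion is likely to turn on it.

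**What to change.** In section 4.3:

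1. Add a random effect on change for TranS-C provider, or for delivery group where sessions were in groups, in a partially nested form, with Satterthwaite or Kenward–Roger degrees of freedom.
2. Assign patients who changed provider by a fixed rule, such as the first assigned provider.
3. Prespecify a sensitivity analysis that allows correlated provider effects in both arms, or uses provider-level cluster-robust standard errors. The partially nested model alone would assume that provider effects are absent in UC-DT.
4. Report the distribution of caseloads, group sizes and the estimated ICC for change.

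The cost is a few lines of SAP text and one more variance term. Sessions are already counted per patient and provider (3.5.1.3), and Aim 3 needs the provider–patient link in any case. Section 6 has assessments continuing to August 2023 and section 4.1 leaves covariates open, so on the plan's own timetable this can still be prespecified. The downsides are slightly wider intervals and the need to confirm that group membership was recorded, which the documents do not say.
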